1.7 Newly Diagnosed Multiple Myeloma (NDMM)

Multiple research paths are being explored in patients with NDMM with a focus on evaluating ixazomib in combination with agents commonly used across treatment settings. The development of ixazomib in combination with lenalidomide with dexamethasone (LenDex) in patients with NDMM who are transplant eligible or ineligible involves 2 studies (C16005 and C16008) with similar study designs except for a few key differences, namely the schedules of ixazomib and dexamethasone. Ixazomib is also being evaluated in combination with melphalan and prednisone (MP) for patients who are not transplant eligible due to age or coexisting morbidity (in Study C16006).

All 3 studies are phase 1/2, with phase 1 focusing on safety and phase 2 on efficacy (and further characterization of safety). Please refer to the ixazomib IB and SMA for further information.

1.8 Clinical Trial Experience Using the Intravenous Formulation of Ixazomib

See the IB for descriptions of the 2 studies that investigated IV ixazomib in advanced solid tumors and advanced lymphoma (Studies C16001 and C16002, respectively).

Version 8 - 2014-0379

1.9 Study Rationale

In adult AML and high-risk MDS patients that achieve remission, the median progressionfree survival is less than 1 year, and most patients will still ultimately die of their disease. Additionally, the median age of AML and MDS of 65 to 70 years of age prevents curative stem cell transplantation procedures in the majority of our patients. Thus additional therapies are warranted at the time of remission to prevent a very high risk of relapse.

Relative to normal hematopoietic cells, AML blasts and leukemic stem cells (LSCs) have higher levels of NFkB activity, which can contribute to pro-survival signaling and chemoresistance. The novel, orally bioavailable, reversible and selective small molecule 20S proteasome inhibitor ixazomib has been shown to induce apoptosis in cancer cells with downregulation of survival proteins including NFkB, phospho-Rb, and Bcl-2. Thus, modulating NFkB activity with ixazomib may represent an important therapeutic approach that can target any residual LSCs at the time of remission.

1.10 Potential Risks and Benefits

Please refer to the current ixazomib IB and SMA.

The clinical benefit of ixazomib continues to be studied in a comprehensive and global development plan that involves studies sponsored by Millennium. Ixazomib appears to show early signs of anti-tumor activity as evidenced by at least 50% reduction in disease burden in some patients, including patients that have been heavily pretreated as well as those with newly diagnosed MM, and prolongs stabilization of the underlying disease in other patients across all ongoing trials. The preliminary findings are favorable when considering historical and currently available therapies for the patient populations evaluated. Though additional data are needed to characterize the clinical benefit of this drug, the emerging data supports expanded development of ixazomib for the treatment of patients with advanced malignancy.

This study will be conducted in compliance with the protocol, good clinical practice (GCP), applicable regulatory requirements, and International Conference on Harmonisation (ICH) guidelines.

20

2. STUDY OBJECTIVES

2.1 Primary Objectives

The primary objective of this study is to determine the efficacy of ixazomib in patients with acute myeloid leukemia (AML) and high-risk myelodysplastic syndrome (MDS) in complete remission (CR) or complete remission with incomplete count recovery (CRi) assessed by improvement on relapse-free survival (RFS).

2.2 Secondary Objectives

The secondary objectives of the study are to determine the efficacy of ixazomib at eradicating MRD (minimal residual disease) as assessed by multiparameter flow cytometry, as well as to determine the safety of ixazomib in this patient population.

2.3 Tertiary/Exploratory Objectives

The exploratory objectives of this study are:

- 1. To evaluate molecular or other genetic features of the patients hematologic malignancy that may be predictive of response
- 2. Correlative laboratory studies of subjects including gene expression profiling and other biomarkers to determine the *in vivo* mechanism of action and biological effects

3. STUDY ENDPOINTS

3.1 Primary Endpoints

The primary efficacy endpoint is relapse free survival (RFS), defined as the interval from the date of the achievement of CR/CRi to the date of first objective documentation of disease relapse or death from any cause. Subjects who are lost to follow-up without documented relapse, or are alive at last follow-up without documented relapse will be censored at the date of their last response assessment.

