5. STUDY POPULATION

5.1 Inclusion Criteria

Each patient must meet all of the following inclusion criteria to be enrolled in the study:

- 1. Male or female patients 18 years of age or older.
- 2. Voluntary written consent must be given before performance of any study related procedure not part of standard medical care, with the understanding that consent may be withdrawn by the patient at any time without prejudice to future medical care.
- 3. Female patients who:

Confidential

- Are postmenopausal for at least 1 year before the screening visit, OR
- Are surgically sterile, OR
- If they are of childbearing potential, agree to practice 2 effective methods of contraception, at the same time, from the time of signing the informed consent form through 90 days after the last dose of study drug, OR
- Agree to practice true abstinence when this is in line with the preferred and usual lifestyle of the subject. (Periodic abstinence [eg, calendar, ovulation, symptothermal, post-ovulation methods] and withdrawal are not acceptable methods of contraception.)

Male patients, even if surgically sterilized (ie, status post-vasectomy), must agree to one of the following:

- Agree to practice effective barrier contraception during the entire study treatment period and through 90 days after the last dose of study drug, OR
- Agree to practice true abstinence when this is in line with the preferred and usual lifestyle of the subject. (Periodic abstinence (eg, calendar, ovulation, symptothermal, post-ovulation methods] and withdrawal are not acceptable methods of contraception.)
- Patients must have a history of *de novo* or therapy-related AML (defined by WHO classification of ≥20% bone marrow blasts) or high-risk MDS (defined by IPSS or IPSS-R)
- Patients must be in a documented CR/CRi from either their front-line or first salvage therapy as evidenced by <5% bone marrow blasts and absence of extramedullary disease. (For patients with prior MDS who then transformed to AML, therapy received for MDS is not considered prior therapy for AML)
- 6. Patients should have received at least 2 cycles of induction therapy or 1 induction and 1 consolidation cycle, OR patient should be considered to have completed all planned chemotherapy, OR patient is considered to be unable, unfit or unwilling to receive additional chemotherapy.
- 7. Eastern Cooperative Oncology Group (ECOG) performance 0, 1, or 2.
- 8. Patients must meet the following clinical laboratory criteria:

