7.1.1 Determination of Sample Size and Futility Monitoring

Futility will be monitored for the study. We will monitor RFS using the methods of Thall et al. (2005), and we will stop enrolling patients to the study if we have reason to believe that the median RFS is less than that from the historical data, which is around 11 months. The trial will be stopped if Pr(lamda(E) > lamda(S) | data from the trial) < 0.05, where lamda(S) is the median RFS for standard treatment in the historical data with an inverse gamma distribution IG(123, 1342), which corresponds to a mean of 11 months and a standard deviation of 1 month, the corresponding 95%CI of (9.2, 13.1) months. The prior for lamda(E) is assumed to be IG(3.21, 24.31), corresponding to a mean of 11 months and a larger standard deviation of 10. Futility monitoring will start once 10 patients have been enrolled. Assuming an accrual rate of 1 per month and an additional follow-up of 12 months, the operating characteristics for the futility stopping rule under various true states are summarized in the following table 1, with results based on 5000 simulations.

Median OS (M)	Prob(Stop Early)	Mean No. of Patients
		(25%, 75%)
17	0.012	39.6 (40, 40)
14	0.036	39.1 (40, 40)
11	0.164	36.8 (40, 40)
8	0.673	28.2 (17, 40)

Table 1: Operating characteristics for futility monitoring

5	1	14.2 (10, 17)

Multc Lean V2.1 and OneArmTTE Version 4.1.1 were used for the trial design. The Department of Biostatistics will provide and maintain a website ("Clinical Trial Conduct": https://biostatistics.mdanderson.org/ClinicalTrialConduct/) for futility monitoring for each treatment arm on this study. The Clinical Trial Conduct website resides on a secure server, and access is gained through usernames and passwords provided to personnel responsible for enrolling patients and updating patient data. The website is accessed through a browser using secure socket layer (SSL) technology. Personnel responsible for enrolling patients on trials, which includes the principal investigator(s), research nurse(s), and data coordinator(s), will be trained by members of the Department of Biostatistics in the use of the trial website; the importance of timely updating of follow-up times and recording of events will be emphasized in training.

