7.1.4 Efficacy Analysis

It is expected that the median RFS time will be 11 months or higher under this study treatment. If the trial continues to maximum accrual of 40 patients and maintains sufficient follow-up to observe 25 events (relapse/death) with a median RFS of 11 months, then a 95% credible interval for median RFS would extend from 7.4 to 16.3 months. The median RFS time will be estimated by Bayesian posterior estimates, along with the 95% credible intervals.

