7.1.8. Study Endpoints

Relapse-Free Survival (RFS):

Is defined as the interval from the date of enrollment to the date of first objective documentation of disease relapse or death from any cause. Subjects who are lost to follow-up without documented relapse, or are alive at last follow-up without documented relapse will be censored at the date of their last response assessment.

Overall Survival (OS):

Time from date of treatment start until date of death due to any cause.

Complete Remission (CR):

Peripheral counts: No circulating blasts, neutrophil count $\ge 1 \ge 1 \ge 10^{9}$ /L and platelet count $\ge 100 \ge 10^{9}$ /L Bone marrow: $\le 5\%$ blasts, no detectable auer rods, no extramedullary leukemia with normal maturation of all cell lines. Persistent dysplasia will be noted.

Complete remission with incomplete count recovery (CRi):

Defined as a morphologic complete remission but the ANC may be $<1 \ge 10^9$ /L or the platelet count may be $<100 \ge 10^9$ /L.

Time to discontinuation from treatment will be assessed as an estimate of treatment failure/tolerability and is defined as the interval from the date of enrollment to the date of discontinuation. Subjects who are ongoing in treatment at the time of study closure will be censored at the date of last visit.

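### The primary endpoint RFS starts at CR/CRi in Section 3.1 but at enrollment in Section 7.1.8, and the 11-month benchmark has no stated start date or population, so the futility rule can err in either direction

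*Combined protocol and SAP*

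**What the plan says.** - Section 3.1 has RFS "defined as the interval from the date of the achievement of CR/CRi to the date of first objective documentation of disease relapse" or death.
- Section 7.1.8 says of the same endpoint: "Is defined as the interval from the date of enrollment to the date of first objective documentation of disease relapse" or death. The event and the censoring rule match Section 3.1; only the start differs.
- Section 7.1.1 stops enrollment if there is reason to believe that "the median RFS is less than that from the historical data, which is around 11 months". Its comparator, lamda(S), "is the median RFS for standard treatment in the historical data", with distribution IG(123, 1342). It gives no start date, source or population for that median.
- Section 7.1.4 uses the same figure: "It is expected that the median RFS time will be 11 months or higher under this study treatment".
- Section 1.9 says that in "patients that achieve remission, the median progressionfree survival is less than 1 year". It gives no start date and is not linked to the 11 months.
- Section 5.1, on eligibility: "Patients must be in a documented CR/CRi from either their front-line or first salvage therapy". Sections 5.1 and 5.2 set no upper limit on time since remission. No section describes delayed entry (left truncation).

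**The concern.** A patient can enroll only if still alive and in remission, so nobody can have an event between CR/CRi and enrollment. Under Section 3.1 that interval counts as follow-up; under Section 7.1.8 it does not. The same patient therefore yields two different RFS times. Staff enter follow-up times into the monitoring website, and nothing tells them which time to enter.

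The trial has one arm, so the efficacy inference rests on comparing RFS with 11 months. If the trial and the benchmark do not share an origin and a population, the futility rule may keep a drug that is worse than history or stop one that equals it. An origin left open until the data are seen is also open to selection.

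**Working it through.** **Inputs.** From Section 7.1.1: prior IG(3.21, 24.31) for the trial median; benchmark IG(123, 1342); stop if Pr(lamda(E) > lamda(S) | data) < 0.05; monitoring from 10 patients; accrual of 1 per month; 12 further months of follow-up; 40 patients at most. My assumptions: a gap of 1, 2, 3 or 6 months, equal for all patients; a look at each enrollment from 10 patients; a final look at the end of follow-up.

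**Formulas.** With exponential RFS, d events and total counted time T, the posterior is IG(3.21 + d, 24.31 + ln2 × T), with mean (24.31 + ln2 × T)/(2.21 + d). With a = 3.21 + d and b = 24.31 + ln2 × T, Pr(lamda(E) > lamda(S)) is the F(2a, 246) distribution function at 123b/(1342a).

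**The plan's own figures first.** IG(123, 1342) has mean 1342/122 = 11.0, SD 1.0 and 95% interval 9.2 to 13.1, as stated. Simulation with no event-free time counted (40,000 trials per scenario, Monte Carlo SE at most 0.0025):

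| True median (months) | 17 | 14 | 11 | 8 | 5 |
|---|---|---|---|---|---|
| Pr(stop), Table 1 | 0.012 | 0.036 | 0.164 | 0.673 | 1 |
| Pr(stop), reproduced | 0.011 | 0.034 | 0.157 | 0.672 | 1.000 |
| Mean patients, Table 1 | 39.6 | 39.1 | 36.8 | 28.2 | 14.2 |
| Mean patients, reproduced | 39.7 | 39.2 | 36.8 | 28.0 | 14.3 |

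**Effect on the estimate, by hand.** Take the 25 events and 11-month median of Section 7.1.4. Then ln2 × T = 25 × 11 = 275, and the posterior mean is (24.31 + 275)/27.21 = 11.0. Counting a 3-month gap for 40 patients adds 120 months to T and 0.693 × 120 = 83.2 to the numerator: 382.5/27.21 = 14.1. The drug has not changed. In the simulated trials, followed to the end with about 33 events, the posterior mean at a true post-enrollment median of 11 goes from 11.1 to 11.9/12.7/13.5/15.9 for gaps of 1/2/3/6 months. IG(123, 1342) appears nowhere in this calculation.

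**Effect on the futility rule.**

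| Pr(stop) for an assumed gap of | none | 1 month | 2 months | 3 months | 6 months |
|---|---|---|---|---|---|
| (a) Section 3.1, benchmark without lead time, true post-enrollment median 8 | 0.67 | 0.43 | 0.21 | 0.07 | 0.00 |
| (b) Section 7.1.8, benchmark from CR in patients still in remission, no drug effect | 0.16 | 0.27 | 0.44 | 0.67 | 1.00 |

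In (a), T is follow-up plus the gap. In (b), T is follow-up only, and a no-effect drug has a post-enrollment median of 11 minus the gap: 10/9/8/5 months. Gaps that vary between patients (exponential, same means) give 0.43/0.22/0.09/0.00 in (a). Without the final look, the no-gap value at median 8 is 0.62, (a) becomes 0.38/0.17/0.05/0.00 and (b) becomes 0.25/0.41/0.62/1.00. The pattern does not change.

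**Delayed entry.** If time is counted from CR/CRi but patients are at risk only from enrollment, T under the exponential model equals the enrollment-origin T. The results are therefore those with no gap, by construction. This matches a benchmark in all patients who reach CR only at constant hazard. For a no-effect drug with Weibull times, CR-origin median 11, a 3-month gap and such a benchmark:

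- Shape 0.7: Pr(stop) about 0.05 and posterior mean about 16. With no gap these are about 0.22 and 13.
- Shape 1.3: Pr(stop) about 0.44 and posterior mean about 8.8. With no gap these are about 0.16 and 9.9.

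Part of the shift is exponential misfit, as the no-gap values show; the gap adds the rest.

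**The case against.** **The gap may be small.** One entry route in Section 5.1 reads "OR patient is considered to be unable, unfit or unwilling to receive additional chemotherapy", and it allows enrollment soon after remission. This stands: the documents give no gap, and every size above is an illustration. In (a), though, one month is enough to take 0.67 to 0.43.

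**Case (b) needs a benchmark counted from CR in patients who had stayed in remission, and no section describes one.** This also stands. Nor does any section exclude it, and that is the gap in the plan.

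**A single-arm phase II with no formal success test has limited consequences.** In part. The final analysis is an estimate with an interval, but the futility rule is a formal decision that runs on these times.

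**Stronger readings that the documents do not support.** A reader might infer that bias in the RFS estimate depends on the benchmark. It does not: the posterior uses only IG(3.21, 24.31) and the trial data. What matters is the patients to whom the estimate is meant to apply.

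A reader might also infer that Section 3.1 always weakens the rule. It does not. If the benchmark too runs from CR in patients still in remission, Pr(stop) at a CR-origin median of 8 is 0.71/0.78/0.88/1.00 for gaps of 1/2/3/6 months (the last implies a post-entry median of only 2 months). At 11 it is 0.11/0.09/0.07/0.08, with posterior mean 10.9/10.7/10.4/9.4. Table 1 does not describe that setting either, but the rule is not weakened at 8 and RFS is not inflated.

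**Conclusion.** The contradiction is plain in the current text, concerns the primary endpoint and must be fixed. Two conclusions should be kept apart.

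- **Estimate.** From CR/CRi without delayed entry, it includes event-free time and overstates RFS as an estimate for all patients who reach remission. From enrollment, it is a valid estimate of RFS after enrollment.
- **Futility rule and comparison with 11 months.** The error can go either way, and the documents do not settle which, because the benchmark's origin and population are not stated. At an assumed gap of 3 months, the rule's chance of stopping a drug with post-enrollment median 8 could be about 0.07 instead of 0.67, or its chance of stopping a no-effect drug about 0.67 instead of 0.164.

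These sizes rest on assumed gaps, exponential times after enrollment and an assumed look schedule. Table 1 reproduces only when no event-free time is counted. That fits the enrollment clock, and a reader might take it as proof that enrollment was intended. It is not: a CR clock simulated without any gap would give the same table.

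**What to change.** 1. In Section 7.1.1, state the start date and the population of the historical RFS behind IG(123, 1342): all patients who reached CR/CRi, or only those still in remission at a later point.
2. Use one RFS origin, worded identically in Sections 3.1 and 7.1.8, for both futility monitoring and the final analysis. The simplest is enrollment (or first dose), with the benchmark counted from the same point in patients still in remission. If the CR/CRi origin is kept, count time at risk only from enrollment and record each patient's CR/CRi date.
3. Re-derive the prior and re-run Table 1 if the benchmark's origin or population differs from the trial's, if event-free time stays in the count, or if constant hazard is not credible.

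**Cost.** A sentence in Section 3.1 or 7.1.8, a sentence in Section 7.1.1, a check of the historical data, and new simulations only if step 3 applies. Section 5.1 already requires documented remission, but the screening table in Section 6.1 does not list its date, so a CR/CRi origin needs that field. With an enrollment origin, the median will look shorter than RFS counted from CR and will not compare directly with it.

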3.2 Secondary Endpoints

The secondary endpoint is to evaluate the efficacy of ixazomib at eradicating MRD as assessed by multiparameter flow cytometry in those patients who are MRD positive at the start of study.

The safety endpoint will assess overall incidence and severity of all adverse events events using Common Toxicity Criteria v 4.0. The descriptions and grading scales found in the revised NCI Common Terminology Criteria for Adverse Events (CTCAE) most current version will be utilized for adverse event reporting. (http://ctep.cancer.gov/reporting/ctc.html).

3.3 Tertiary/Exploratory Endpoints

The following exploratory endpoints and correlative laboratory studies will be examined to determine the *in vivo* mechanism of action and biological effects of treatment, as well as to detect whether certain molecular or other genetic patterns can predict response to ixazomib:

- Correlation of initial cytogenetic and mutational status (of 28 genes known to be affected in myelodysplastic syndromes and acute leukemias) performed through the bone marrow and molecular diagnostics laboratory of MD Anderson.
- Gene expression profiling and gene-specific DNA methylation may be performed. DNA methylation will be assessed using bisulfite PCR assays (i.e. COBRA or pyrosequencing analysis) and gene expression profiling by real-time PCR analysis.
- Additional exploratory subgroup analyses will be performed where an adequate number of subjects are available in each subgroup to allow for meaningful interpretation of results and these include: age group, sex, race, response (CR vs CRi at start), prior history of MDS (yes/no), cytogenetic category, induction therapy and consolidation therapy received, ECOG performance score.

4. STUDY DESIGN

4.1 Overview of Study Design

This is an open-label single arm Phase II study in subjects with AML or high-risk MDS in CR/CRi. Patients will receive single 4mg oral dose of ixazomib on days 1, 8 and 15 of each 28-day cycle. Treatment with ixazomib will be administered for 12 cycles for patients who remain in CR.

For patients with MRD positive CR/CRi at study start, treatment with ixazomib may continue for a total of 12 cycles after achievement of MRD negativity is observed.

Patients who are experiencing clinical benefit may be eligible to continue therapy after the allotted 12 cycles after discussion with the PI and the discussion documented in the patient's medical record.

Subjects will be assessed for outcome status (i.e. maintenance of CR/CRi) every 3 cycles or as clinically indicated. Adverse events, compliance and concomitant medications will be assessed continually throughout the study; specific information will be requested at each study visit.

Study cycles will be administered every 28 days ± 5 days or upon resolution of any clinically significant study drug related AE to grade 0-1, whichever occurs first.

Administration of subsequent cycles should be administered when neutrophils recover to \geq

0.5 x 10⁹/L and platelets to \geq 50 x 10⁹/L, or to baseline levels prior to the start of the last cycle of therapy.

Ixazomib will be self-administered primarily on an outpatient basis; but may be administered as an inpatient. Patient compliance will be documented using the MD Anderson (MDACC) Research Medication Diary and will be assessed at each study visit.

